## Vital Signs/Orthostatic Vital Signs

Vital signs will be obtained at Screening, Day -1, Day1 (predose, 1hr, 2hr, 4hr, 8hr, 24hr post dose) and Day 2 of each period.

Vital signs will include body temperature, respiratory rate, heart rate and systolic and diastolic blood pressure.

Orthostatic vital signs will be obtained at Screening and Day 1 (predose, 1hr, 2hr) of each period and may or may not include all the vital parameters.

Height, weight and BMI will be measured only at the Screening Visit only.

Actual values of vital signs and changes from baseline will be summarized using descriptive statistics by treatment and time point. Only subjects with both non-missing baseline and time point values will be summarized at each time point.

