#### **Study Endpoints**

**Primary Endpoint:** The pharmacodynamics of lasmiditan as measured by serial vital signs, ECGs, and AEs.

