## 8.4.2 Vital Signs

The continuous outcome variables, vital signs (BP, HR, RR and oral body temperature), will be summarized by treatment (lasmiditan 200 mg co-administered with sumatriptan (lmitrex) 100 mg, lasmiditan 200 mg co-administered with lasmiditan placebo 200 mg, or sumatriptan (lmitrex) 100 mg co-administered with lasmiditan placebo 200 mg) using descriptive statistics. Changes from baseline in vital signs will be summarized by descriptive statistics for each dosing sequence.

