### 2. STUDY DETAILS

# 2.1 Study Objectives

The study objectives are:

**Primary Objective-** To compare and contrast the pharmacodynamics of Lasmiditan 200 mg and Sumatriptan (Imitrex) 100 mg administered together to the pharmacodynamics of single doses of either drug administered alone.

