#### 4. STUDY ENDPOINTS

# 4.1 Pharmacodynamic (PD) Endpoint

Adverse Event and Vital Signs are considered as the pharmacodynamic endpoints in this study. All other PD endpoints will be considered under safety.

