### 6.4.10.2 Electrocardiogram (ECG)

ECG will be obtained at Screening, Day 1 (predose, 1hr, 1.5hr, 2hr, 2.5hr, 4hr, 8hr) Day 2 (24hr) of each treatment period and end of study.

Standard 12-lead ECGs evaluations will include heart rate and interval information such as RR, PQ/PR, QRS, QT, QTcF and QTcB. Overall interpretation (normal, abnormal not clinically significant or abnormal clinically significant) will also be recorded.

For continuous ECG parameters, actual values and changes from baseline will be summarized using descriptive statistics by treatment and time point. For ECG interpretation, the number and percentage of subjects will be summarized by treatment and time point. Additionally, a shift table from baseline to Day 2 will be presented for each treatment.

All ECG data will be provided as a by-subject listing.

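### SAP 6.4.7 plans no within-subject combination-minus-single-drug difference with a confidence interval for vital signs, although the primary objective is that comparison

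*SAP*

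**What the plan says.** SAP 2.1 sets a comparative primary objective, with each drug on its own as the reference: "To compare and contrast the pharmacodynamics of Lasmiditan 200 mg and Sumatriptan (Imitrex) 100 mg administered together to the pharmacodynamics of single doses". Protocol Study Endpoints gives the primary endpoint as "The pharmacodynamics of lasmiditan as measured by serial vital signs, ECGs, and AEs". SAP 4.1 is narrower: "Adverse Event and Vital Signs are considered as the pharmacodynamic endpoints in this study". It moves the remaining pharmacodynamic measures, ECG among them, to safety.

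For vital signs, SAP 6.4.7 states: "Actual values of vital signs and changes from baseline will be summarized using descriptive statistics by treatment and time point". The parameters are listed there: "Vital signs will include body temperature, respiratory rate, heart rate and systolic and diastolic blood pressure". SAP 6.1 defines the descriptive statistics as n, mean, SD, minimum, median and maximum, and takes change from baseline within each period. SAP 6.4.10.2 treats continuous ECG data in the same way: "For continuous ECG parameters, actual values and changes from baseline will be summarized using descriptive statistics by treatment and time point".

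Protocol 8.4.2 is also descriptive. It summarises vital signs by treatment, then adds: "Changes from baseline in vital signs will be summarized by descriptive statistics for each dosing sequence". Protocol 8.3 allows optional 90% confidence intervals on continuous summaries but names no treatment difference.

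**The concern.** Protocol 5.6 assigns every subject all three treatments, in six sequences of seven. Such a design lets each subject serve as his or her own control, and the primary objective asks for exactly that comparison. For blood pressure and heart rate, the planned output is instead one set of summary statistics per treatment and time point. No difference between treatments is formed and none is given an interval.

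Whether adding sumatriptan to lasmiditan changes blood pressure or heart rate beyond either drug alone is a central question of the study. Under the present plan a reader could see a gap of a few mm Hg between two columns and have no planned way to judge how precisely it is known. Anyone who built the contrast later from the listings would choose the model, time point and interval level after seeing the data.

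**Working it through.** **1. Is a contrast planned anywhere?**

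| Place | Between-treatment analysis |
|---|---|
| SAP 6.4.7, vital signs | None; descriptive by treatment and time point |
| SAP 6.1 | Change from baseline within a period, so not a treatment contrast |
| SAP 6.4.10 | Lists vital signs as a safety parameter; adds no analysis of them |
| Protocol 8.3 | Optional 90% intervals on summaries; no difference named |
| Protocol 8.4.1 | A model, for TEAE frequency only |
| Protocol 8.4.2, 8.4.3 | Descriptive |
| Protocol 8.5 | Paired t-test with 90% intervals, for PK only |
| SAP 6.4.9.2 | Geometric mean ratios with 90% intervals, for PK only |

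A secondary objective (PK) therefore gets an estimated treatment difference with an interval. The continuous endpoint under the primary objective does not.

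**2. Is there a planning figure to reproduce?** None concerns vital signs. The only stated power is for PK equivalence: at least 80% with 36 subjects and a 25% within-subject CV. A paired two-one-sided-tests calculation (limits 80-125%, df 35) gives 96.6% at a true ratio of 1.00, 89.5% at 0.95 and 81.5% at 0.93, so the statement is reproducible for ratios near 1. It says nothing about blood pressure.

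**3. What can be recovered from the columns?**

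- *Point difference.* With complete data, mean(C) minus mean(A) equals the mean of the within-subject differences.
- *Precision.* Var(C-A) = SD_C² + SD_A² - 2ρ·SD_C·SD_A. The tables give the SDs but not ρ, the between-period correlation of the changes.
- *Same subjects.* The SAP 6.2.2 PD population needs only one completed period, and SAP 6.4.7 applies its missing-value rule separately at each time point. SAP 3.1 enrols 42 to obtain 36 completers, an allowance of 6. The columns can therefore hold different people.

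**4. How much could pairing matter?** Inputs: n = 36 (SAP 3.1); SD of change 10 mm Hg and ρ from 0 to 0.7, both assumed because the documents give neither.

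- Unpaired half-width = t(70) × SD × √(2/n)
- Paired half-width = t(35) × SD × √(2(1-ρ)/n)
- 95%: t(70) = 1.994, t(35) = 2.030. 90%: t(70) = 1.667, t(35) = 1.690.

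| Case | SE (mm Hg) | 95% half-width | Against unpaired | 90% half-width |
|---|---|---|---|---|
| Unpaired | 10√(2/36) = 2.357 | 4.70 | reference | 3.93 |
| Paired, ρ = 0 | 2.357 | 4.79 | 2% wider | 3.98 |
| Paired, ρ = 0.1 | 10√(1.8/36) = 2.236 | 4.54 | 3% narrower | 3.78 |
| Paired, ρ = 0.3 | 10√(1.4/36) = 1.972 | 4.00 | 15% narrower | 3.33 |
| Paired, ρ = 0.5 | 10√(1/36) = 1.667 | 3.38 | 28% narrower | 2.82 |
| Paired, ρ = 0.7 | 10√(0.6/36) = 1.291 | 2.62 | 44% narrower | 2.18 |

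Half-widths scale with the SD: at 8 and 12 mm Hg the unpaired 95% value is 3.8 and 5.6. The percentages do not depend on the SD, but they depend heavily on ρ. The small loss at ρ = 0 comes only from having 35 rather than 70 degrees of freedom.

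**The case against.** The strongest reply is that descriptive analysis was a deliberate choice. Protocol 8.4.2 is descriptive too, so the SAP drops no vital-sign contrast that had been promised. No hypothesis, margin or sample-size basis concerns vital signs. SAP 6.1 lists data by subject, period, treatment and time point, so the differences can be formed later. All of this is true. It argues against demanding a formal test. It does not meet a comparative objective, and a contrast built from listings is not pre-specified.

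Second, change from a period-specific pre-dose value already removes each subject's stable level. The correlation that remains between changes may be low, and the gain from pairing could then be negligible. This stands, and it is why the table starts at ρ = 0.

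Third, modelling everything yields many intervals. Three parameters × 5 post-dose times × 2 contrasts is 30. Adding QTcF and ECG heart rate at 7 post-dose times gives 2 × 7 × 2 = 28 more, 58 in all. This stands as a reason to rank them in advance.

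A reader might also infer three things that the documents do not support:

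- *That Protocol 8.4.2 pools the three treatments.* It says changes are summarised for each dosing sequence but not that periods are merged within a sequence. The SAP already summarises changes by treatment.
- *That pairing would cure dropout.* It keeps the same subjects on both sides. If the missing subjects' unusual response is specific to the combination, the complete-pair estimate shifts as the column mean does.
- *That no interval of any kind is foreseen.* Protocol 8.3 permits them on summaries, though optionally and not for a difference.

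**Conclusion.** The point holds as an omission: for a pharmacodynamic endpoint under a comparative primary objective, no within-subject C-A or C-B estimate with an interval is pre-specified in either document. This rests on the text and on no assumed figure. The table shells were not available to check.

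It would go too far to conclude that the report cannot say how large the added effect is. With complete data the difference of mean changes is that point estimate. What is missing is its precision, and the assurance that both sides rest on the same subjects.

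The gain in precision is conditional. With 36 completers it runs from about 2% wider at ρ = 0 to 44% narrower at ρ = 0.7, or 4.79 to 2.62 mm Hg against 4.70 unpaired at an assumed SD of 10 mm Hg. Even with no gain, the reader would have a planned estimate and a valid interval. This is a change that should be made; it is not a flaw in the design.

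**What to change.** Add to SAP 6.4.7, for change from the period's pre-dose value in supine SBP, DBP and HR, a mixed model with treatment, period and sequence as fixed effects and subject as a random effect. Report C-A and C-B with confidence intervals, as estimation without formal tests. Use the 90% level already in Protocol 8.3, Protocol 8.5 and SAP 6.4.9.2, or justify 95%. Name in advance one main time point or summary per parameter, which gives 3 × 2 = 6 main intervals, and call the rest supportive. Keep the descriptive tables.

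QTcF and ECG heart rate may be handled the same way in SAP 6.4.10.2. That section should acknowledge that the protocol lists ECG under the primary endpoint while SAP 4.1 moves it to safety.

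The cost is SAP wording and a few programmed tables, with no new subjects, visits or measurements. The downside is several additional intervals, which must be labelled as estimation.

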#### 6.4.8 Pharmacokinetic Analysis

Calculation of PK parameters will be performed using Phoenix® WinNonlin® version 6.4 (or later). Statistical analysis and generation of summary tables and listings will be performed in SAS.

All PK analyses will be performed on the PK population.

#### 6.4.9 Plasma PK Concentrations

Blood samples for determination of plasma concentrations will be collected on Day1 and Day 2 for each treatment period and at the time points indicated in the following table:

Day(s)	PK Collection Time Points
Day 1	Pre-dose and 0.25, 0.5, 1, 1.5, 2, 2.5,3,
	4, 6, 8, 12, and 16, hours post-dose
Day 2	24 and 30 hours following the Day 1
	dose of IMP

Plasma concentrations that are below quantification limits (BQL) will be treated as follows in the pharmacokinetic analyses and clearly identified in listings.

- 1. If it is a leading BQL treat as 0 (zero)
- 2. If it a middle BQL treat missing value (depending on the situation)
- 3. If it is a tailing BQL, treat as missing valve.

Descriptive statistics of Lasmiditan, and Sumatriptan plasma concentrations will be presented for each treatment period and timepoint. The statistics will additionally include geometric mean and CV (%). All plasma concentrations will be listed.

Figures (linear and semi-logarithmic) illustrating the relationship between time after study drug administration and plasma drug concentrations will be created for each subject and for the mean results.

#### 6.4.9.1 PK Parameter Estimation

Pharmacokinetic parameters  $C_{max}$ ,  $T_{max}$ ,  $AUC_{0\text{-tlast}}$ ,  $AUC_{0\text{-inf}}$ ,  $t_{1/2}$ ,  $\lambda_z$ , CL/F, Vz/F will be estimated. The exact time of sample collection, relative to time of dose, will be used in the analyses. No imputation of missing samples will occur. If a scheduled sample's concentration is missing, the pharmacokinetic analyses will be conducted as if that sample had not been scheduled for collection. The time of dosing will be considered as time 0 and the pre-dose assessment will be treated as if it occurred at time 0. Any subject with sufficient data to adequately characterize their concentration-time profile will be included in the pharmacokinetic analyses. If the terminal half-life for any case is physiologically implausible, and a suitable set of terminal concentrations cannot be selected from the semi logarithmic concentration-time plot, then no elimination parameter estimates will be reported.  $t_{1/2}$  can only be estimated for those cases where the apparent elimination rate constant has been estimated.

Descriptive statistics will be presented for each PK parameter for each study medication by treatment period (Lasmiditan and, Sumatriptan). All PK parameters will be listed.

#### 6.4.9.2 Pharmacokinetic Statistical Inference

The PK parameters, Cmax and  $AUC_{0-tlast}$  and  $AUC_{0-\infty}$  will be the primary PK analysis variables. An ANCOVA model will be fit for log-transformed PK parameter ( $C_{max}$  or  $AUC_{0-tlast}$   $AUC_{0-\infty}$  separately) as the outcome, with the fixed effect of treatment group. From this model, least square (LS) Means for each treatment and LS Mean differences to the reference drug Lasmiditan will be estimated with the corresponding 90% confidence intervals. These estimates will then be exponentiated to produce the estimates of geometric mean ratios (Combination vs standalone PK for lasmiditan and sumatriptan) with their 90% confidence intervals. It will be concluded that the IMP has no effect on PK, if 90% confidence intervals for combination/standalone is within the 80-125% interval.

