# 5.6 Randomization and Blinding

This is a randomized, double-blind, three-period, cross-over, study to investigate the effect of single doses of sumatriptan (Imitrex) 100 mg on the pharmacodynamics of a single dose of lasmiditan 200 mg. The dosing periods are:

- A: Lasmiditan 200 mg co-administered with lasmiditan 200 mg placebo
- B: Sumatriptan (Imitrex) 100 mg co-administered with lasmiditan 200 mg placebo
- C: Lasmiditan 200 mg co-administered with sumatriptan (Imitrex) 100 mg

The study will be conducted at a single center. Subjects will be randomized using a Williams square design to one of six treatment sequences, as follows:

ABC	ACB
BAC	BCA
CAB	CBA

Seven of the planned 42 subjects will be included in each treatment sequence. The design is balanced for period and first order carryover effects.

Double-blinding will be accomplished as follows:

- Dosing staff, comprised of an unblinded pharmacist or designee (who prepared the medication), an unblinded dosing assistant, and an unblinded registered nurse (RN) will administer all study medications. They will have no other role in the trial and will not communicate their activities in the trial to other staff involved in the trial in any way.
- Investigational product, prepared in the Pharmacy by an unblinded Pharmacist
  or designee, will be dispensed from the Pharmacy in an amber medication vial
  (with a subject specific label blinded to the identity of the investigational
  product) to the unblinded dosing staff and dosed to the subject directly from the
  amber vial to the subject's mouth.
- Prior to dosing, each subject will be blind-folded and will remain blind-folded until the hand and mouth check has been completed. Curtains will be drawn around the bed prior to dosing and will remain in place until the hand and mouth check has been completed. No one will enter the curtained space other than the subject, the unblinded RN, and the unblinded dosing assistant.

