## 8. STATISTICAL METHODS

Before database lock, a statistical analysis plan (SAP) will be issued as a separate document, providing detailed methods for the analyses outlined below.

Any deviations from the planned analyses will be described and justified in the final integrated clinical study report.

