# 8.5 Pharmacokinetic Analyses

All evaluable subjects will be included in the PK analysis. The evaluable PK population will include all subjects who completed at least one treatment period without any protocol violations that would likely affect the PK results, who have evaluable plasma concentration data for lasmiditan and/or sumatriptan (Imitrex), and for whom at least a subset of the designated PK parameters can be determined.

Data will be summarized using descriptive statistics (sample size, mean, median, standard deviation, minimum, and maximum) for continuous variables and using frequency and percentage for discrete variables for each treatment unless additional analysis is deemed appropriate based upon a review of the PK results.

Standard PK parameters ( $C_{max}$ ,  $t_{max}$ ,  $t_{1/2}$  and AUC [AUC(0-last) and AUC(0-∞)] of lasmiditan 200 mg will be used to describe the characteristics of the drug when co-administered with sumatriptan (Imitrex) or when taken alone.

The primary statistical analysis will use the paired t-test applied to log-transformed PK parameter (lasmiditan Cmax or AUC30 separately) in the lasmiditan/sumatriptan (Imitrex) treatment period paired with the same subject's parameter value in the lasmiditan treatment period. From this model the means for each treatment and mean differences to the reference lasmiditan treatment will be estimated with the corresponding 90% confidence intervals. These estimates will then be exponentiated to produce the estimates of geometric mean ratios with their 90% confidence intervals. It will be concluded that sumatriptan (Imitrex) has no effect on lasmiditan PK, if 90% confidence intervals for ratios of PK parameters derived in lasmiditan/sumatriptan (Imitrex) treatment period to those derived in lasmiditan treatment period are within the 80-125% interval.

The sample size of 36 subjects will provide at least 80% power to show equivalence of the PK of lasmiditan in the absence and presence of sumatriptan (Imitrex), assuming a 25% within subject coefficient of variation.

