# 2.2 Study Design

This is a Phase 1, single-center, randomized, double-blind, three-period, cross-over study to investigate the effect of single doses of Sumatriptan (Imitrex) 100 mg on the

pharmacodynamics of single doses of Lasmiditan 200 mg. A total of 42 subjects will be enrolled to ensure at least 36 subjects complete the study with approximately 60% females.

The three dosing periods are as follows-

- A: Lasmiditan 200 mg co-administered with Lasmiditan 200 mg placebo
- B: Sumatriptan (Imitrex) 100 mg co-administered with Lasmiditan 200 mg placebo
- C: Lasmiditan 200 mg co-administered with Sumatriptan (Imitrex) 100 mg

Subjects are randomized using the William square design into one of the six treatment sequences ABC, ACB, BAC, BCA, CAB, CBA.

The study will last approximately 6 weeks including up to 3 weeks for screening and 22 days on study. Screening will be conducted within approximately 21 days of the first dose of study medication. Each dosing period will last 3 days (Day -1, Day 1, and Day 2). A wash-out period of 6 days will take place between each dose. The End of Study Visit (EoS) will take place 5 (+/- 2) days after the third dosing period is completed.

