#### 3. DATA ANALYSIS CONSIDERATIONS

# 3.1 Determination of Sample Size

The sample size calculation for this study is based on the proportion of adverse events in the two treatment groups namely the combination therapy (Lasmiditan + Sumatriptan) vs a single drug (Lasmiditan). The calculation is performed using a test for two proportions in a repeated measures design. To ensure that at least 36 subjects complete, 42 subjects (approximately 60% female) will be enrolled.

The sample size of 36 subjects will provide at least 80% power to show equivalence of the PK of Lasmiditan in the absence and presence of Sumatriptan (Imitrex), assuming a 25% within subject coefficient of variance.

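### The SAP's PK equivalence model names treatment as its only effect, so its 90% CI ignores the crossover pairing and the stated 80% power no longer follows

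*SAP*

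**What the plan says.** Protocol 8.5, repeated in the synopsis, reads: "The primary statistical analysis will use the paired t-test applied to log-transformed PK parameter". It names lasmiditan Cmax and AUC30 and pairs each subject's value on the combination with that subject's own value on lasmiditan alone. No effect is concluded if the 90% CI for the ratio lies within 80-125%.

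SAP 6.4.9.2 keeps the 90% CI and the 80-125% rule but changes the model. It fits an ANCOVA to log Cmax, AUC0-tlast and AUC0-∞, each "as the outcome, with the fixed effect of treatment group". No covariate, subject, period or sequence term, random effect or repeated-measures structure is named there or elsewhere in the SAP.

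The design is not in doubt. SAP 2.2 states: "Subjects are randomized using the William square design into one of the six treatment sequences". Protocol 5.6 adds: "The design is balanced for period and first order carryover effects".

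On power, SAP 3.1 says: "The sample size of 36 subjects will provide at least 80% power to show equivalence of the PK of Lasmiditan", and gives the variability as "assuming a 25% within subject coefficient of variance". The same section also says: "The sample size calculation for this study is based on the proportion of adverse events".

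On changes of method, Protocol 8 says: "Any deviations from the planned analyses will be described and justified in the final integrated clinical study report". The SAP gives no reason for leaving the paired t-test.

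**The concern.** In a crossover, each subject's two log values share that subject's own level, and the pairing removes it from the comparison. A model with treatment alone leaves it in the residual. The estimated standard error of the treatment difference then reflects between-subject plus within-subject variance, although the difference itself varies only with the within-subject part. The nominal 90% interval is too wide whenever the between-subject variance is above zero.

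The 80-125% rule is applied to that interval, so a true absence of interaction may fail to be shown. The SAP also contradicts itself: its power statement uses a within-subject CV, which describes the error term only if subject is in the analysis.

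**Working it through.** **Inputs from the documents.** 36 completers and within-subject CV 25% (SAP 3.1); limits 80-125% and a 90% CI, i.e. two one-sided tests at 5% (SAP 6.4.9.2).

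**Assumptions.** The between-subject CV (CVb) and the true ratio are not given. I take CVb of 20% to 50% and true ratios of 1.00 and 0.95. All figures are for one parameter with complete pairs.

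**Log-scale quantities.**
- Margin: ln(1.25) = 0.2231.
- Within-subject variance: ln(1 + 0.25²) = 0.0606.
- Between-subject variance: ln(1 + CVb²) = 0.0392, 0.0862, 0.1484 and 0.2231 at CVb 20, 30, 40 and 50%.
- True standard error of the mean difference under either model: √(2 × 0.0606/36) = 0.0580.

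**Step 1: the plan's own figure, with the paired analysis.** CI half-width = t(0.95, 35) × 0.0580 = 1.690 × 0.0580 = 0.098. Power is 96.6% at ratio 1.00, 89.4% at 0.95 and 81.5% at 0.93. The claim of at least 80% is reproduced for true ratios in that range (at 0.925 power is 79.0%).

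**Step 2: the SAP model as written.** For lasmiditan, treatments A and C give 72 values and 70 residual degrees of freedom. The pooled variance estimates the between-subject plus the within-subject variance, so

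half-width = t(0.95, 70) × √(2 × (between + 0.0606)/36), with t(0.95, 70) = 1.667.

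At CVb 40%: 1.667 × √(2 × 0.2090/36) = 1.667 × 0.1078 = 0.180.

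I obtained power, coverage and the false-equivalence rate from the normal distribution of the mean difference, averaged over the two independent chi-square variances (2,000,000 draws). Direct simulation agrees within 0.5 percentage point.

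| CVb | Half-width | Power, ratio 1.00 | Power, ratio 0.95 | True coverage of 90% CI | False equivalence at ratio 1.25 |
|---|---|---|---|---|---|
| Paired (any CVb) | 0.098 | 96.6% | 89.4% | 90% | 5.0% |
| 20% | 0.124 | 90.8% | 78.7% | 96.4% | 1.8% |
| 30% | 0.151 | 77.9% | 62.5% | 98.8% | 0.6% |
| 40% | 0.180 | 53.6% | 39.8% | 99.7% | 0.16% |
| 50% | 0.209 | 23.8% | 16.9% | 99.9% | 0.04% |

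**Step 3: where the claim breaks.** Treatment-only power equals 80% at CVb 28.8% (ratio 1.00) and 18.9% (ratio 0.95).

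**Step 4: what this means for the decision.** At CVb 40% the interval is 0.180/0.098 = 1.83 times as wide. To pass, the observed log ratio must lie within ±(0.2231 − 0.180) = ±0.043, a ratio of about 0.957 to 1.044. With the paired analysis the range is ±(0.2231 − 0.098) = ±0.125, or 0.882 to 1.133. At a true ratio of 0.95, the treatment-only model needs about 49 completers (CVb 30%) or 64 (CVb 40%) for 80% power.

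**The case against.** The strongest reply is that the model statement is incomplete rather than wrong. Calling it an ANCOVA implies a covariate, naming a fixed effect suggests that a random one may exist, and the power statement uses a within-subject CV. If a subject term is in the code, the loss of power disappears. That may be so, but the text does not say it. A second programmer following SAP 6.4.9.2 would fit treatment alone and get a different interval.

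Several other points stand as limits on the concern:
- The size of the loss depends on a CVb that the documents do not give. At a low CVb the SAP model still reaches 80%.
- 42 subjects are enrolled. If all 42 were evaluable, power would be 80.1% at CVb 35% (ratio 1.00), although still 79.5% at CVb 25% (ratio 0.95).
- Protocol 8 places the justification of deviations in the study report, so the SAP's silence breaches no rule.
- The paired t-test has no period or sequence term either. The omission that matters is the subject term.
- PK is a secondary objective, and with complete pairs the estimated ratio is the same under both models.
- The same data can be re-analysed at any time. That is a reason to settle the model before results are seen, not to leave it open.

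**Conclusion.** The concern holds. As written, the SAP model omits the subject term that a crossover needs, departs from the protocol's paired t-test without a stated reason, and does not support the PK power claim in SAP 3.1. This does not show that power is below 80%: that happens only above a CVb of about 29% (true ratio 1.00) or 19% (true ratio 0.95), with 36 completers and 25% within-subject CV.

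The direction is conservative. The false-equivalence rate falls below its nominal 5%, and the cost is over-wide intervals and a possible failure to conclude no effect when there is none. This should be fixed, but it does not threaten the primary objective.

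**What to change.** Rewrite the model statement in SAP 6.4.9.2 so that each log parameter is analysed within subject, separately for lasmiditan and sumatriptan, with the 90% CI taken from within-subject error. Either of these will do:

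1. Restore the protocol's paired t-test, C versus A, for lasmiditan and apply the same test, C versus B, to sumatriptan. The sumatriptan comparison extends the protocol's inferential test, which covers lasmiditan only, and the SAP should say so.
2. Specify a mixed model with fixed sequence, period and treatment and random subject within sequence. State the reason for departing from the protocol, and keep the paired t-test as a sensitivity analysis.

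If a subject term was always intended, adding it to the model statement is enough. In the same edit, state how subjects with only one of the two relevant periods are handled, since the SAP's PK population admits them and a paired test drops them. Also reconcile the protocol's AUC30 with the SAP's AUC0-tlast and AUC0-∞.

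The cost is SAP wording and a few lines of SAS, with no new data, subjects or visits.
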